## I. BACKGROUND AND SIGNIFICANCE

Non-insertional Achilles Tendinopathy (AT) is a common overuse injury in adults who are both athletes and nonactive. Tendinopathy occurs when there is either a failed healing response or the failure of normal turnover or remodeling response. AT can result in pain and limited movement due to the injury.

In the last few decades there has been an increased prevalence of people running to maintain a healthier lifestyle. With an increase in running, there has been an increase in running-related injuries. Of these running-related injuries, AT contributes to between 6.2% and 9.5%. It's been estimated in some studies that burden of AT may reach 52% lifetime prevalence in runners.

The most common treatment of choice for AT now are exercise loading programs. Eccentric strengthening (ECC), although the current most prominent treatment, may only improve symptoms in approximately 60% of AT patients.

Laser-induced photobiomodulation (PBM) has been shown to increase cell proliferation and metabolism, which may aid in the repair and remodeling process. Photobiomodulation therapy (PBMT) has been shown to be effective in a variety of clinical settings depending on wavelength and parameters used. In a meta-analysis and systematic review on plantar fasciitis, it was found that PBMT is effective with exercise and without exercise. Tumilty et al. found that PBMT was effective in the treatment of AT, but it was more effective when paired with exercise sessions, however other studies have shown mixed results.

Extracorporeal shockwave therapy (ESWT) is a process in which energy is delivered to the muscles or tendons to relieve aches and pains. Like PBMT, ESWT is used to treat a variety of musculoskeletal conditions, however it is more expensive and therefore used less often. A recent network meta-analysis showed that in the long term when ECC was combined with ESWT it was effective in treating AT, however there is limited data available on the impacts of ESWT in short term recovery. Notably PBMT was not able to be compared in the analysis due to no published studies meeting criteria for inclusion. There is also limited information available on the best energy settings to be used in treating AT, and therefore more research needs to be done into the impact of ESWT on treating AT.

PBMT and ESWT are effective treatments, and a study on the treatment of other tendons in the body - lateral epicondylitis (tennis elbow) - showed improvement in both the PBMT and the ESWT arms, with ESWT showing a significant difference in increasing handgrip strength. Studies such as this are promising that ESWT and PBMT will be effective in treating other tendon injuries such as AT. This promising result combined with the previous unclarity in the best treatment for AT justifies the need for more research. The sub-section of AT amongst runners has had very limited research and given the high prevalence, is something that should be addressed. Therefore, our study will compare three different treatment arms utilizing SWT, PBMT and traditional physical therapy, and using both questionnaires and measured outcomes we will assess the most effective treatment for AT.

## II. SPECIFIC AIMS

The primary aim of this pilot study is to evaluate the **effects** of standard physical therapy compared to treatment with SWT, and a combination of SWT and PBMT (each combined with physical therapy) in the management of Achilles tendinopathy. *We hypothesize runners in each treatment allocation will see improvement in functional outcomes, pain and measures of Achilles tendon structure compared to baseline measures. As SWT and PBMT may change structural properties and modulate pain in tendinopathy, we anticipate greater measures in running function for participants assigned to SWT and PBMT in treatment over physical therapy as sole treatment.*

The secondary outcome will be to evaluate cross-over response. After the initial 3-month randomized control trial, subjects who are not satisfied with results, will be able to select a different treatment arm for the remaining 3 months of the study.

## III. SUBJECT SELECTION

### a. Inclusion/Exclusion Criteria

#### Inclusion Criteria

Patients will be eligible if they meet the following criteria:

- Patients aged between 18-65 years old with a diagnosis of mid-portion Achilles tendinopathy (including both unilateral and bilateral)
- Running is the pre-injury primary form of physical activity and pre-injury would complete on average 10 miles per week or more of running
- VISA-A <80 at baseline to be eligible

#### Exclusion Criteria

Exclusion criteria includes:

- Less than 3 months of symptoms
- Primary insertional Achilles tendinopathy
- Diagnosis of rheumatological disease/connective tissue condition, symptomatic arthritis of foot and ankle, a primary running related injury outside Achilles tendinopathy, other contraindications to PBMT or SWT
- Have received SWT within the past 3 months to their Achilles
- Prior injection within 3 months
- Currently enrolled in PT for more than 4 weeks for their condition
- Women who are pregnant or **those who are planning to become pregnant**. This is due to the fact that pregnancy will reduce participants activity after the treatment and the safety concerns related to shockwave treatment.
- Patients with neuropathy affecting sensation to pain
- Patients with a known underlying cardiac disease that could be affected by shockwave therapy
- Patients with known history of Achilles tendon rupture
- Patient currently taking oral steroids or fluoroquinolone antibiotics

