**V. STUDY PROCEDURE**

**a. Overall Research Design and Methods**

This study has been split into two parts. **Part 1 is the initial randomized control trial, and Part 2 is when the participants can select the treatment they want to receive if they are not satisfied with their initial treatment.** In Part 1 patients will not be blinded to the treatment arm that they receive due to the obvious differences in the treatments.

Participants will also be asked to log their return to running at home using the University of Delaware Return to Sport protocol.

*Part 1*

Study participants will be randomly assigned to one of three treatment groups, using a block randomization generator **that is implemented into REDCap**. There will be 20 patients per treatment group, no power calculation as this is a feasibility study. The three treatment arms are: physical therapy only, SWT and physical therapy, and a combination of SWT, PBMT and physical therapy. All runners, regardless of treatment group, will be asked to enroll in physical therapy at a location that is convenient to them (and accepts their insurance if applicable) and complete a standard physical therapy program addressing individual strength deficits in both proximal (spine and hip girdle) along with distal (thigh, leg and foot/ankle) muscle groups. To standardize loading program, we will provide all runners with an at-home exercise program designed by [name] for progressive Achilles tendon loading. This will be

completed alongside the physical therapy they are receiving. Activities including running will be allowed as tolerated following published guidelines by [name].

In subjects who have bilateral AT, the leg with the most severe symptoms (determined by the VISA-A) will be chosen as the primary data for the study, however both legs will be treated consistent with the treatment group the subject was randomized into. Outcomes will be obtained for each Achilles tendon, regardless of treatment, using VISA-A at each data collection point. Participants will also be asked to complete a weekly log of running and completing PT exercises.

## Part 2

At the 3-month follow-up, participants who are not satisfied with their outcome will be given the option to choose one of the remaining treatment arms. Regardless of what treatment a patient chooses, if any, there will be one final visit conducted at 6 months for final data collection.

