\*At baseline subjects will be screened for their eligibility using the inclusion and exclusion criteria described on page 2 of this document. To determine pregnancy female patients will be asked if they are pregnant, **planning to become pregnant**, or not **pregnant**. MGB guidelines state that when using non-iodizing radiation if a woman states she is not pregnant, no pregnancy test is required.

Due to the nature of COVID-19, in-person visits, check-ins, and questionnaires, can be rescheduled +/- 14 days within each of the outlined study timepoints.

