### **Shockwave**

The OrthoPlus Ultra 100 is a Class I FDA approved device with minimal risk. It is a low energy device and no severe events have been reported.

Reported discomforts of shockwave include bruising, swelling and rarely, tissue damage. Pain response is expected due to device treatment over sites of injury and use of process of clinical focusing; we will monitor each patient and adjust treatment settings to ensure pain is tolerable during the treatment.

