### **Photobiomodulation**

The risks associated with PBMT are minimal. Mild discomfort may be experienced during the treatment, the treatment should not be “hot”, but participants should notify the study team member if they feel any uncomfortable warming. Individuals with neuropathies or difficulty distinguishing changes in skin temperature are at higher risk. Protective eyewear will be provided and must be worn by the participant and study team member during operation of the laser to protect your eyes from accidental laser exposure. No serious adverse events have been reported using this treatment.

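### The only explicit sensory exclusion is for pain, which is narrower than the group the protocol itself places at higher risk from photobiomodulation

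*Combined protocol and SAP*

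**What the plan says.** Section III.a, Exclusion Criteria, rules out "Patients with neuropathy affecting sensation to pain". A separate bullet in the same list ends with a general exclusion for "other contraindications to PBMT or SWT". The supplied text does not list or define those contraindications.

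Section VII, under Photobiomodulation, opens with "The risks associated with PBMT are minimal" and adds that no serious adverse events have been reported. It then states: "Individuals with neuropathies or difficulty distinguishing changes in skin temperature are at higher risk". For the session itself it says that "participants should notify the study team member if they feel any uncomfortable warming".

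Under Shockwave, the same section describes a safeguard based on pain: "we will monitor each patient and adjust treatment settings to ensure pain is tolerable during the treatment".

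On screening, the footnote to Table 1 in section V.b says: "At baseline subjects will be screened for their eligibility using the inclusion and exclusion criteria described on page 2 of this document". On later exposure, section V.a (Part 2) says that at 3 months "participants who are not satisfied with their outcome will be given the option to choose one of the remaining treatment arms".

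**The concern.** An entry rule and a risk statement in the same protocol describe different groups of people. The risk statement covers neuropathies in general and also poor discrimination of skin temperature. The entry rule covers only neuropathy that dulls pain.

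The difference matters because of how the PBMT session is protected. A participant who does not sense warmth well is less able to give the early report that section VII asks for. What is at stake is the safety of an individual in the treatment session, and consistency between screeners: two careful people applying the list could reach different decisions on the same candidate. No estimate, test or comparison in section VI is at stake.

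**Working it through.** No arithmetic applies. The plan states no figure on this point and has no power calculation. The check is to set the entry criteria against the risk statement for each kind of candidate.

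| Candidate | In the section VII higher-risk group? | Named in the section III.a sensory bullet? | Reached by the general contraindications bullet? |
|---|---|---|---|
| Neuropathy that reduces pain sensation | Yes | Yes, excluded | Not needed |
| Neuropathy that reduces temperature sensation, pain preserved | Yes | No | Left to judgement |
| Poor discrimination of skin temperature without a neuropathy diagnosis, pain preserved | Yes | No | Left to judgement |
| Neuropathy affecting neither pain nor temperature sensation | Yes, on the plain wording | No | Left to judgement |

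1. *Does the general bullet settle rows two to four?* It would if section VII called these conditions contraindications, or if the contraindications were listed. Section VII speaks only of higher risk, and no list appears. Exclusion is therefore allowed but not clearly required.

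2. *Does the gap touch the safeguard?* For rows two and three, yes, in part. The participant is asked to report uncomfortable warming, and weak temperature sensation blunts that report. Pain sensation is intact in those rows, so discomfort can still be felt. For row four the stated safeguard is unaffected.

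3. *Who could be exposed?* The combination arm takes 20 of the 60 participants by randomisation. The other 60 − 20 = 40 can reach PBMT only if they are dissatisfied at 3 months and choose that arm.

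4. *What else limits harm?* The description of the combined arm in section V.a sets the dose at 10 J/cm², has staff calculate the treatment time, and uses a hand piece that governs delivery speed. The operator is the investigator or a trained staff member. Section IX.a has side-effects documented at each visit, and section VI.a provides per-limb interviews about expected adverse events from week 1. These records detect a reaction but do not prevent one during the session.

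**The case against.** The strongest reply is that the plan already handles this. Everyone is screened against the whole list, the general bullet lets an investigator turn such a candidate away, and the way the list is introduced does not make it exhaustive. Section VII is a risk disclosure, and nothing obliges a protocol to exclude every group at higher risk, least of all when it regards the baseline risk as minimal. Much of this stands. It is why the point is a cheap improvement and not a defect that has to be corrected. It does not remove the mismatch, because the decision still rests on an undefined phrase.

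Three stronger readings are tempting, and the documents do not support them.

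- *That the protocol contradicts itself by admitting people it regards as contraindicated.* It never calls impaired temperature sensation a contraindication.
- *That the pain bullet was written for shockwave and leaves PBMT with no sensory protection.* The bullet is not tied to either device, whereas the cardiac exclusion names shockwave expressly. Pain sensation is also relevant to PBMT, since the warming to be reported is uncomfortable warming.
- *That nobody asks about temperature sensation at screening or before Part 2.* The supplied text describes no such question, but the screening forms, the consent pages and appendix I were not available. Silence in the remaining text is weak evidence.

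**Conclusion.** The point holds as a low-level safety and eligibility matter. The explicit sensory exclusion is narrower than the protocol's own PBMT risk group, and the general bullet reduces the gap without closing it.

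The number affected is probably very small or zero. It takes a runner whose temperature sensation is impaired while pain sensation is preserved, who is not turned away on judgement, and who then receives PBMT. That is a judgement: the documents give no prevalence, and nothing in them would anchor an expected count. The conclusion also assumes that no definition of contraindications or sensory question sits in the material not supplied. If one does, the gap may already be closed in practice and only the wording needs to follow. A reader should not infer that the treatment is unsafe or that any between-arm result is biased.

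**What to change.** Reword the sensory bullet in section III.a along these lines: *patients with lower-limb neuropathy affecting sensation (pain or temperature), or with difficulty telling changes in skin temperature*. This closes the second and third rows of the table. It leaves the fourth open deliberately, because the stated safeguard works for those people. The lower-limb qualifier follows the treated area, from the knee fold to the sole. It is not in the current bullet, so the sponsor should omit it if neuropathy elsewhere is also meant to exclude.

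Apply the criterion once, at baseline screening. Anyone who could choose PBMT in Part 2 has already passed that screen, so a repeat at 3 months would add little.

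The cost is one reworded bullet and a matching question at screening. The downside is possibly a very few extra screen-outs.

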## IV. SUBJECT ENROLLMENT

### a. Recruitment Procedure

We hope to enroll 60 runners into three treatment arms (n=20 in each arm). We will be using a multi-pronged approach to recruit patients:

- Running Clinics
  - Referral from [name]
  - Referrals from other physicians at MGB and Harvard affiliated hospitals
    - A letter and flyer will be provided to other practitioners in the MGB network to ask them to refer our study information to their patients.
- Social Media
- Email Lists
  - Flyers to be sent to different email lists of running clubs
- Hospital advertising
  - Flyers
  - Rally
  - Research Patient Data Registry (RPDR)

**b. Procedure for obtaining informed consent**

A member of the research study staff will introduce the study to the patient and if they express interest in the study, then they can have the informed consent explained to them. Patients will have as much time as necessary to consult with their family or their physicians before enrolling in the study. If the patient understands and accepts the document, it will be signed, and the subject will be enrolled. No treatment or data collection will be done without informed consent. Consent can be obtained by any member of the study staff who has been trained in Good Clinical Practice (GCP). If a potential study subject is a patient of the PI, [name], then consent will be obtained by a different trained study staff member to avoid any concern for coercion. Consent may be gained in person or using the MGB online database – REDCap.

**V. STUDY PROCEDURE**

**a. Overall Research Design and Methods**

This study has been split into two parts. **Part 1 is the initial randomized control trial, and Part 2 is when the participants can select the treatment they want to receive if they are not satisfied with their initial treatment.** In Part 1 patients will not be blinded to the treatment arm that they receive due to the obvious differences in the treatments.

Participants will also be asked to log their return to running at home using the University of Delaware Return to Sport protocol.

*Part 1*

Study participants will be randomly assigned to one of three treatment groups, using a block randomization generator **that is implemented into REDCap**. There will be 20 patients per treatment group, no power calculation as this is a feasibility study. The three treatment arms are: physical therapy only, SWT and physical therapy, and a combination of SWT, PBMT and physical therapy. All runners, regardless of treatment group, will be asked to enroll in physical therapy at a location that is convenient to them (and accepts their insurance if applicable) and complete a standard physical therapy program addressing individual strength deficits in both proximal (spine and hip girdle) along with distal (thigh, leg and foot/ankle) muscle groups. To standardize loading program, we will provide all runners with an at-home exercise program designed by [name] for progressive Achilles tendon loading. This will be

completed alongside the physical therapy they are receiving. Activities including running will be allowed as tolerated following published guidelines by [name].

In subjects who have bilateral AT, the leg with the most severe symptoms (determined by the VISA-A) will be chosen as the primary data for the study, however both legs will be treated consistent with the treatment group the subject was randomized into. Outcomes will be obtained for each Achilles tendon, regardless of treatment, using VISA-A at each data collection point. Participants will also be asked to complete a weekly log of running and completing PT exercises.

## Part 2

At the 3-month follow-up, participants who are not satisfied with their outcome will be given the option to choose one of the remaining treatment arms. Regardless of what treatment a patient chooses, if any, there will be one final visit conducted at 6 months for final data collection.

### Physical Therapy Only Arm

After enrollment, participants will be assigned the home exercise program from [name] and physical therapy with a therapist of their choice, instructions will include addressing any other lower extremity impairments known to contribute to Achilles tendinopathy including proximal strengthening program. The treatment protocol from Silbernagel et al. (2017) is described below:

#### *Phase 1: Week 1 – 2 (perform exercises every day)*

- Pain-monitoring model information and advice on exercise activity
- Circulation exercises (moving foot up/down)
- 2-legged toe raises standing on the floor (3 sets × 10-15 repetitions/set)
- 1-legged toe raises standing on the floor (3 × 10)
- Sitting toe raises (3 × 10)
- Eccentric toe raises standing on the floor (3 × 10)

#### *Phase 2: Week 3 – 5 (Perform exercises every day)*

- 2-legged toe raises standing on edge of stair (3 × 15)
- 1-legged toe raises standing on edge of stair (3 × 15)
- Sitting toe raises (3 × 15)
- Eccentric toe raises standing on edge of stair (3 × 15)
- Quick-rebounding toe raises (3 × 20)

#### *Phase 3: Week 3 – 12 (Perform exercises every day and with heavier load 2-3 times/week)*

- 1-legged toe raises standing on edge of stair with added weight (3 × 15)
- Sitting toe raises (3 × 15)
- Eccentric toe raises standing on edge of stair with added weight (3 × 15)
- Quick-rebounding toe raises (3 × 20)
- Plyometric training

#### *Phase 4: Week 12 – 6 months (Perform exercises 2-3 times/week)*

- 1-legged toe raises standing on edge of stair with added weight (3 × 15)
- Eccentric toe raises standing on edge of stair with added weight (3 × 15)
- Quick-rebounding toe raises (3 × 20)

Patients when working with their physical therapist, may be at different stages in their rehabilitation, continued physical activity/sport may be performed without a negative effect on recovery if the guidance on pain level and perceived exertion scale laid out by [name] is

followed. Patients do not need to stop their activities as long as the activity is modified according to the pain monitoring model, and recovery days are adjusted accordingly.

**Shockwave (SWT) Arm:**

The shockwave arm will receive shockwave treatment in addition to the physical therapy program from [name]. They will receive one treatment a week and one telephone check-in a week for three weeks. [name], the PI, will perform the SWT on all study participants, using the OrthoPlus Ultra 100/radial D-Actor. This Extracorporeal Pressure Activation Treatment (EPAT) device will be used at a radial shockwave of 3000 counts treatment settings of 15 Hz minimum 2 bars with a focus applicator head at mid-portion of Achilles using clinical focusing technique, and 3000 counts at 15 Hz minimum 2.5 bars using broad oscillator to myotendinous region and over symptomatic areas of gastrocnemius and soleus. Maximal settings will be 4 bars and initial treatment will start at 500 strikes at 1.5 bars for each treatment head to allow participant to be comfortable as we start shockwave sessions. The research coordinator will conduct the telephone calls to check-in on physical therapy exercise compliance and response to each treatment.

